6.3.2 Blinding Procedures

No blinding procedure are performed in this study.

6.4 Unblinding Procedures (Code break)

n.a.

7 STUDY POPULATION

7.1.1 Inclusion Criteria

Participants fulfilling all of the following inclusion criteria may be enrolled in the study:

Inclusion criteria:

- Healthy
- 18-45 years old
- shoe size 5,6,9 or 10

7.1.2 Exclusion Criteria

The presence of any one of the following exclusion criteria will lead to exclusion of the participant:

Exclusion criteria:

- injuries of the lower limbs
- previous surgeries on the lower limbs
- neuromuscular disorders
- restriction in gait capabilities
- current medical treatment

7.2 Recruitment and Screening

Enrollment is planned for a period of 2 months. Direct recruitment of potential study participants, contact between the study team and potential subjects in person. Volunteers giving written informed consent will be assessed during the visit at the institute of biomechanics.

There will be no payment given as compensation for time and effort of the participants. To ensure gaining baseline data for each gender the aim is to enroll ten men and ten women.

7.3 Assignment to Study Groups

Not applicable. Data will only be acquired in only one study group. All participants will be tested in all three interventions.

7.4 Criteria for Withdrawal/ Discontinuation of Participants

Each subject has the right to withdraw from the study at any time without prejudice. If a subject withdraws, the reason(s) will be documented.

Should a participant feel uncomfortable or exhausted during the measurements, the procedure can be discontinued anytime. In case of withdrawal during the measurement or withdrawal after the measurement, the data still will be evaluated so the study doesn't lose its value. Although the data and the material will be anonymised which means that anonymization key will be deleted for this subject so nobody can track down the data to the according subject. In case of too much invalid trials due to too short step length or similar unforeseen incidents which lead to insufficient amount of data, the Sponsor-Investigator will initiate the recruitment of an additional subject to prevent the loss of the study's value.

8 STUDY INTERVENTION

8.1 General Information

For each subject a gait analysis involves: 5 valid trials on level and on ramp walking with the study intervention, the reference intervention and the control intervention.

8.1.1 Study Intervention

Study Intervention A

The stability boot Ortho® Tri-Phase is a product of Künzli SwissSchuh AG.

8.1.2 Reference Intervention

Study Intervention B

The stability boot VACOped® from OPED AG.

8.2 Administration of Study Intervention and Reference Intervention

8.2.1 Study Intervention

The Ortho® System ensures, according the producer, right amount of stability. Through the calculated softness of the boot mobility is warranted. The boot assures an early functional and early weight bearing of the injured foot. The stability boot Ortho® Tri-Phase is a product of Künzli SwissSchuh and a postoperative/conservative therapy for ankle injuries as distortion, arthrodesis, chronic ankle instability or calcaneus and ankle fractures. A modular joint should ensure a restriction of the ankle joint. The boot can be individually adapted. The modular extractable ankle support has according to the three healing phases three different stages and restricts the joint in the two planes (frontal and sagittal). In the first phase the boot should restrict the range of motion in the ankle joint 10°, in the second phase 30° and in the third there is no limitation. During all phases the boot limits the Inversion/Eversion movement in the frontal plane. Due to wearing the new stability boot in pairs a healthy gait symmetry and the preservation of body statics is ensured. For each of the gait conditions (ramp up, ramp down and level walking) and each restriction of the stability boot (10°, 30° and free) the subject has to perform five valid gait trials. (Künzli, 2015)

8.2.2 Reference Intervention

The VACOped® dynamic vacuum ankle orthosis product of OPED and treats like the OTP ankle fractures, metatarsal and calcaneus fractures, distortions, prosthetics, arthrodesis but additionally it is a therapy for achilles tendon ruptures. OPED promises that an early weight bearing of the injured foot will be possible. The boot gives option to adapt the range of motion of the sagittal plane from -15° to +30°. It should shorten the recovery time and therefore early mobility will be ensured. Moreover, an earlier risk free weight bearing of the foot counteract atrophy and ensures a soon return to work. The developed vacuum cushion adapts to individual patients anatomy and can be modified to fit swelling and atrophy. Other than the Ortho Tri-Phase® the VACOped® is worn only on one foot. For each of the gait conditions (ramp up, ramp down and level walking) and each restriction of the stability boot (10°, 30° and 45°) the subject has to perform five valid gait trials. (Oped, 2016)

8.2.3 Control Intervention

The control intervention is an indoor shoe. It will serve as a reference to participants normal gait parameters. Every subject does have his own pair of indoor shoe, which it will bring to the visitation.

8.2.4 Modification of Interventions

n.a.

8.3 Compliance with Intervention

n.a.

The observer knows which intervention the subject wears.

Data Collection and Follow-up for Withdrawn Participants

Each subject has the right to withdraw from the study at any time without prejudice. If a subject withdraws, the reason(s) will be documented.

Should a participant feel uncomfortable or exhausted during the measurements, the procedure can be discontinued anytime. In case of withdrawal during the measurement or withdrawal after the measurement, the data still will be evaluated so the study doesn't lose its value. Although the data and the material will be anonymised which means that anonymisation key will be deleted for this subject so nobody can track down the data to the according subject. In case of too much invalid trials due to too short step length or similar unforeseen incidents which lead to insufficient amount of data, the Sponsor-Investigator will initiate the recruitment of an additional subject to prevent the loss of the study's value.

[figure not shown]
8.5 Concomitant Intervention(s)

n.a.

STUDY PROCEDURES

This study involves one dynamic data acquisition synchronized optical motion capture with measurements of ground reaction forces during level walking and ramp walking. The expected total time involvement for each participant maximally adds up to 3 hours.

Study Flow Chart/Table of Study Procedures and Assessments 9.1

Ortho Tri-Phase with 10°, 30° and free ROM in the ankle	VACOped with 10°, 30° and 45° ROM in the ankle
level walking	level walking
ramp up	ramp up
ramp down	ramp down

9.2 Assessments of Outcomes

9.2.1 Assessment of Primary Outcome

Optical motion capture by means of passive reflective skin markers:

The optical motion capture system used in this project corresponds to a conventional motion capture system, i.e. Vicon motion analysis system (Oxford Metrics Group, UK). The method consists in attaching 62 small passive reflective markers on the skin using hypoallergenic tape. Up to 20 fixed and 12 movable cameras register the 3D coordinates of the markers during movement with a capture frequency of up to 2000Hz. The markers are small (1-2cm diameter) and very light, and they do not affect the participants gait or well-being.

The kinematic data of the skin markers will be reconstructed using Vicon Nexus 1.7.1. The markers have to be visible in at least two cameras for reconstruction. Two models, the subject model and a model for the moving fluoroscope will be used. Automatic labeling as well as manual correction will be applied. All relevant gait events will be set. This means more gait events will be set than necessary for defining the 5 valid trials. The "heel strike" events will be set at the first frame the force vector appears on the force plate and the "toe off" events at the first frame the force vector disappears. The force vector is displayed if the force exceeds the 25 N threshold. The Data will be saved as a C3D-file.

Ground reaction force measurements:

Ground reaction forces, i.e. the forces that the subject exerts with the foot to the ground, are measured by six force plates (Kistler Instrumentation, Switzerland) embedded in the ground of the movement analysis laboratory. Additionally, two mobile force plates are installed in a staircase for the measurement of the stair activity. Force measurements and motion capture take place simultaneously and are at all times synchronised.

The origin of the lab coordinate system is equal to the origin (mid-point) of the third force plate B3. Force data as well as the resulting center of pressure (COP) will be described in each force plate's coordinate system. The exact origins and orientations of the mobile force plates will be calculated using the positions of four calibration markers. All force data will be transformed from the respective force plate coordinate system to the lab coordinate system and saved as a C3Dfile with the corresponding kinematic data.

COP values will be corrected by our in-house calibration procedure performed for each force plate [15-17]. The corrected COP values are only estimated for vertical forces larger than 100N. Further data processing of the generated C3D-files and text-files to conduct the calculation of the outcome parameters will be done using Matlab (R2012a, The MathWorks, Inc., Natwick, USA).

Ground Reaction Force Outcome Parameters:

First and second peak (Fz2, Fz4), minima (Fz3), loading (bn) and unloading rate (en) of the ground reaction forces are defined according to Stacoff et al. (2007) (Figure 1).

[figure not shown]

[figure not shown]
Figure 1: Definition of ground reaction force parameters (Stacoff et al., 2007)

Time-Distance-Parameters: For level walking gait velocity is defined as the mean horizontal velocity of the sacrum marker over the whole gait cycle. For ramp gait velocity is described as the mean horizontal as well as vertical velocity of the sacrum marker over the whole gait cycle.

Motion Capture Outcome Parameters:

Skin marker based ankle, knee and hip rotations are described with respect to functionally estimated joint coordinate systems (distal relative to proximal segment).

Joint	Plane	Parameter	
	sagittal	_	a_ROM
Ankle	Sagittai	df1	_
		-	a_ROM
		pf	
		-	a_ROM
		df2	
	frontal	-	a_ROM
		invev	
	transverse	-	a_ROM
		adab	

·	a_ROM pf	dorsiflexion in stance ROM between peak of maximal ankle	[°]
	a_ROM df1	dorsiflexion in stance and peak of maximal plantarflexion beginning of swing ROM between peak of maximal plantarflexion beginning of swing and peak	[°]
a_ROM adab		of maximal ankle dorsiflexion in swing. the maximal and the minimal reached values o	f ankle
	adduction/abduc	tion at any time. [°]	
a_ROM invev	Range between the maximal and the minimal reached values of ankle inversion/eversion at any time. [°]		

Table 1: Motion capture outcome parameters

9.2.2 Assessment of Secondary Outcomes

Every subject's weight and height will be measured at the day the research will be conducted. During the acquisition of the daily activities two video cameras are used to record the subject's execution of the task. This is done to retrace the motion in case of odd results to assure no false data will be integrated in the study. This is the only use for these videos and they will be stored and anonymised as all other data.

9.2.3 Assessment of Safety Outcomes

n.a.

9.2.3.1 Serious Adverse Events

n.a.

9.2.3.2 Laboratory Parameters

n.a.

9.2.3.3 Vital Signs

n.a.

9.2.4 Assessments in Participants who Prematurely Stop the Study

This study only involves one visit for each participant with a gait analysis during dynamic activities (total acquisition time up to 4 hours). Based on our experience, we do not anticipate early termination if a subject complies with all the inclusion/exclusion criteria and has given written consent to participate in the study. Should a participant feel uncomfortable or exhausted during the dynamic video-fluoroscopic measurements, the procedure can be discontinued anytime.

9.3 Procedures at Each Visit

9.3.1 Visit 1

- Participant Information and Informed Consent
- Change into shorts, t-shirt
- Completion of the biometric data by measuring weight and height
- Place 62 small passive reflective markers on the skin using hypoallergenic tape

according to standard gait analysis protocol

The test procedure, consisting of basic motion tasks and 21 dynamic trials (dynamic trials) assessed simultaneously with the motion capture systems and the force plates.

For each of the gait conditions (ramp up, ramp down and level walking) and each restriction of the stability boots (10°, 30° and 45°/free) the subjects have to perform five valid trials. In total there are at least 21*5 trials. A gait trial is considered valid, when the foot is in the field of view of the image intensifier during stance and swing phase and the force plate is hit for level and ramp gait.

Basic motion tasks (each task performed twice):

- Standing trial in an anatomic upright position
- Calibration (Standing in upright position, followed by free movement of legs and arms)
- Four motion tasks to functionally define joint axes and joint centers: dorsi/plantar flexion motion of the ankle, inversion/eversion motion of the ankle, flexion/extension motion of the knee, varus/valgus angle of the knee, hip circumduction (List et al., 2012)

Dynamic trials (five valid gait cycles for each activity):

- Level walking
- Ramp up walking
- Ramp down walking

10 SAFETY

The Sponsor's SOPs provide more detail on safety reporting.

During the entire duration of the study, all serious adverse events (SAEs) that may be causally related to the study intervention are collected and documented in source documents. Reportable events are recorded in the case report form (CRF). Study duration encompassed the time from when the participant signs the informed consent until the last protocol-specific procedure has been completed, including a safety follow-up period.

10.1 Definitions

Adverse events

Adverse events (AEs) are defined as any untoward medical occurrence in a patient or clinical investigation participant after the intervention and which does not necessarily have a causal relationship with this treatment. An AE can therefore be any favorable and unintended sign (including an abnormal laboratory finding), symptom, or disease temporally associated with the intervention, whether or not related to the intervention. An AE may also consist of a new disease, an exacerbation of a pre-existing illness or condition, a recurrence of an intermittent illness or condition, a set of related signs or symptoms, or a single sign or symptom.

Serious Adverse Event

A serious adverse event is defined as any event which:

requires inpatient treatment not envisaged in the protocol or extends a current

- hospital stay;
- results in permanent or significant incapacity or disability;
- is life-threatening or results in death; or
- causes a congenital anomaly or birth defect.

10.2 Recording and Assessment of Serious Adverse Events

The investigator has the responsibility for SAE identification, documentation, and assessing the causal relationship study intervention.

All SAEs will be fully documented in the appropriate CRF. For each SAE, the investigator will provide the onset, duration, treatment required, outcome and action taken with regard to the study intervention.

The assessment by the investigator with regard to the study intervention relation is done according to the following definitions:

Unrelated	 The event started in no temporal relationship to the medical intervention applied and
	 The event can be definitely explained by underlying diseases or other situations.
Related	 The event started in a plausible temporal relationship to the medica intervention applied and
	 The event cannot be definitely explained by underlying diseases or other situations.

10.3 Reporting of Serious Adverse Events

Safety measures that must be taken during conducting the measurement to protect the study participant as well as the underlying circumstances will be reported within seven days by the Sponsor-Investigator to the Ethics Committee.

In case of appearance of a safety related event concerning one of the recruited subjects while conducting the measurement, it will be discontinued immediately. The occurrence of a safety related event and its connection to the Data collection will be reported within seven days by the Sponsor-Investigator. Furthermore the Sponsor-Investigator suggests a further proceeding to the ethics committee.

The Sponsor-Investigator will report the completion or the abortion of the study to the ethics committee within 90 days.

If, in the course of a clinical trial, serious adverse events occur in participants in Switzerland, and it cannot be excluded that the events are attributable to the intervention under investigation, the investigator must report these events:

• to the KEK within 15 days.

Safety and protective measures

If immediate safety and protective measures have to be taken during the conduct of this clinical trial, the investigator must notify the KEK of these measures, and of the circumstances necessitating them, **within 7 days**.

First aid will be provided from the investigators and the following report procedure will be conducted:

Reporting an emergency at ETHZ

Where? Location of the accident (building, floor, room no.)

What? Type of emergency situation

Who? Name of the person reporting/contact details

When? Time of the incident

How many? Number of patients (and their injuries)

What else? Any other imminent hazards

Incident

Someone has been injured or needs medical attention. The kind of incident requires help from the First Aid Team or healthcare professionals.

What to do

1. Alert the Emergency Desk (cf. reporting model)

From internal phones 888

From external phones [name]

The Emergency Desk will mobilise the First Aid Team and, if need be, call an ambulance.

2. Perform first aid

Assist the First Aid Team.

3. Direct the ambulance

If an ambulance is called, helpers need to wait for it at the agreed location to guide it in and show the paramedics the quickest route to the casualty/casualties.

What else?

If you report an incident to the external emergency services, make sure to notify the Emergency Desk too. As a hub for emergencies at ETH Zurich, it must be informed of all incidents.

Minor injuries

Bandage material is provided in the corridors and first-aid stations in all ETH-Zurich buildings. The storage sites are marked with a white cross on a green background.

Uncertainty about the severity of an injury or complications
Consult the doctor.

Eye injuries (chemical spatter etc.)

Consult the doctor immediately.

Annual Safety Report

All SAEs will be summed up in the **annual safety report (ASR)** and submitted to the KEK. ASR shall contain:

- A summary of events including severity and causal relationship to the intervention and on the safety of participants.
- The accompanying letter provided with the Annual Safety Report should contain a short summary of the status of the clinical trial in Switzerland (number of centers open/closed, number of patients recruited/recruitment closed, and number of SAEs).

10.4 Follow up of (Serious) Adverse Events

Participants terminating the study (either regularly or prematurely) with

- reported ongoing SAE, or
- any ongoing AEs of laboratory values or of vital signs being beyond the alert limit will not return for a follow-up investigation.

11 STATISTICAL METHODS

In order to obtain reasonable levels of both Type I and Type II errors, the required number of subjects (sample size) will be estimated using the power analysis approach.

11.1 Hypothesis

The null hypothesis will be that the kinematics in terms of range of motion of flexion/extension and the inversion/eversion of the ankle will not differ between the Ortho Tri-Phase® (Künzli SwissSchuh AG) and the VACOped® (OPED AG). The alternative hypothesis will be that the kinematics in terms of range of motion of flexion/extension and the inversion/eversion of the ankle will differ between the Ortho Tri-Phase® (Künzli SwissSchuh AG) and the VACOped® (OPED AG).

11.2 Determination of Sample Size

The pilot study of Bürgi & Lorenzetti (2015) was used to estimate the study sample size of 20. The mean ankle angle of the prototype with its first ankle joint restriction stage was 16.5 and with its second stage 18.6. Significance level (α) set at 0.05 and power (1- β) at 0.8. σ is the expected standard deviation of 2.7.

The study will be terminated once the satisfactory power is reached with the estimated sample size.

11.3 Planned Analyses

The statistical analyses will be performed using SPSS statistical analysis software. The level of significance for all analyses will be set to P=0.05.

11.3.1 Datasets to be Analyzed, Analysis Populations

The acquired data of all subjects will be included in the analysis. The kinematics data will be divided into 9 subgroups according to the motion tasks that are level walking, ramp up walking and ramp down walking and the three various joint restrictions of the ankle.

11.3.2 Primary Analysis

The primary analysis in this study will be the power-analysis conducted with the null hypothesis, the error of the first kind α =0.05, the error of the second kind β =0.20 and consequently the power 1- β =0.80.

The gait analysis parameters will be described using standard descriptive statistics. Comparison between the stability boots among its outcome measures will be performed by analysis of variance tests.

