6.3 Methods of Minimizing Bias

6.3.1 Randomization

If the participant has to wear the VACOped® or the Ortho Tri-Phase® first will be randomized. Through technical reasons the indoor shoe cannot be randomized.

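### Section 11.3.2 names a power analysis as the primary analysis, and the ANOVA beside it has neither a stated within-participant structure nor a named contrast that decides hypothesis 11.1

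*Combined protocol and SAP*

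**What the plan says.** Section 11.3.2, headed Primary Analysis, opens with "The primary analysis in this study will be the power-analysis conducted with the null hypothesis" and then lists only alpha 0.05, beta 0.20 and power 0.80. Its second paragraph adds descriptive statistics and one sentence on the test: "Comparison between the stability boots among its outcome measures will be performed by analysis of variance tests". The synopsis (Statistical Considerations) repeats the ANOVA and adds nothing on its form. Section 11.3.3 (Secondary Analyses) is marked not applicable.

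The null hypothesis in section 11.1 is that "the kinematics in terms of range of motion of flexion/extension and the inversion/eversion of the ankle will not differ" between the two boots.

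On design, section 7.3 says "All participants will be tested in all three interventions", and section 6.3.1 says "If the participant has to wear the VACOped® or the Ortho Tri-Phase® first will be randomized". The boot data are therefore paired, with randomised order.

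On the outcomes that could be tested:
- Table 1 in section 9.2.1 lists three sagittal ankle range-of-motion (ROM) parameters and one for inversion/eversion, a_ROM invev ("Range between the maximal and the minimal reached values of ankle inversion/eversion at any time").
- Section 11.3.1 says "The kinematics data will be divided into 9 subgroups according to the motion tasks" and the three joint restrictions.
- Section 9.1 gives the third setting as free on the Ortho Tri-Phase and 45° on the VACOped.
- Section 11.3 says "The level of significance for all analyses will be set to P=0.05".

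**The concern.** A power analysis is a design calculation and already has its own place in section 11.2. Naming it as the primary analysis leaves hypothesis 11.1 without a designated test.

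Reading the ANOVA as primary does not close the gap. Four things remain unstated:
- whether the model carries a participant term;
- which ROM parameter, setting, task or pooled boot effect decides 11.1;
- whether 11.1 is rejected when both motions differ, or when either does;
- whether the third setting, which is not the same on the two boots, enters the comparison.

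Two things are at stake. One significant result among several could be reported as rejecting 11.1. And the error rate and power of the boot test depend on a model that the plan does not give.

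**Working it through.** **1. The plan's own figure.** Section 11.2 gives means 16.5 and 18.6 (difference 2.1, between two stages of one prototype, not between the two boots), SD 2.7, alpha 0.05, power 0.80 and N = 20.
- One-sided, unpaired: 2 × [2.7 × (1.645 + 0.842) / 2.1]² = 20.4, so 21 per condition, close to 20.
- Two-sided, unpaired: 26 (normal) or 27 (t).
- Two-sided, paired, with 2.7 as the SD of differences: 13 (normal) or 16 (t).
- A two-sided paired t-test with 2.7 per condition gives 20 only at a correlation of about 0.31, which the documents do not give.

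Section 11.2 therefore does not reveal which analysis is intended. The closest match is one-sided and unpaired, which fits neither the non-directional alternative in 11.1 nor the one-group design.

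**2. Multiplicity.** Suppose any one p < 0.05 is read as rejecting 11.1. With k independent tests and no true difference, the chance of a false positive is 1 − 0.95^k.

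| Assumed analysis | k | Independent | Correlation 0.8 (assumed) |
|---|---|---|---|
| One boot effect for each of two motions | 2 | 9.8% | 8% |
| One for each of four ROM parameters | 4 | 18.5% | 11% |
| Two motions × nine subgroups | 18 | 60% | 23% |

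The last column is from simulation. The 18-test row requires separate testing in each subgroup, which section 11.3.1 does not state. If 11.1 requires both motions to differ, having two motions adds no inflation.

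**3. Pairing ignored, one value per boot per person.** Take N = 20, SD 2.7 per condition and difference 2.1. For the paired test the SD of differences is 2.7 × √[2(1 − ρ)], and the noncentrality is 2.1 × √20 divided by that SD, with 19 df. At an assumed ρ = 0.5 the SD of differences is 2.7 and the noncentrality 3.48, so power is 91%. An independent-groups test on the same data has 73% power and a type I error of 0.8% (simulation). At ρ = 0 the paired test has 65% and the independent-groups test 67%, so pairing gains nothing. If 2.7 is already the SD of differences, which section 11.2 leaves open, paired power is again 91%.

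**4. Participant structure ignored, nine cells per boot pooled.** Total variance is set to 1, with participant share 0.5, participant-by-boot share s and residual 0.5 − s (all assumed). The true variance of the boot difference is 2 × [s/20 + (0.5 − s)/180]. An ANOVA without participant takes it to be about 2 × 1/180 = 0.0111.
- s = 0: the true value is 0.0056, half of what the model takes, so the test is conservative.
- s = 0.2: the true value is 0.0233, about twice what the model takes, so the test is anti-conservative.

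Simulated type I error under a true null, 20 participants:

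| s | No participant term | Participant intercept only | Paired test on participant means |
|---|---|---|---|
| 0 | about 1% | 5% | 5% |
| 0.05 | 4–5% | 15–16% | 5% |
| 0.1 | 9% | 24–25% | 5% |
| 0.2 | 19% | 39% | 5% |

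Of these models, only the paired test on one value per boot holds its level throughout.

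**The case against.** The strongest reply is that this is loose wording. The ANOVA stands under the Primary Analysis heading, section 11.3.3 is not applicable, the synopsis gives ANOVA as the comparison, and sections 6.3.1 and 7.3 make the paired design plain to any analyst. The aim is to describe and compare, and section 11.4 calls this a pilot study. Much of this stands: the ANOVA is probably what is meant. But correcting the label still leaves the model and the deciding contrast undefined, and a plan that states null and alternative hypotheses, alpha and power has to say what decides them.

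A reader might infer more than the documents support:
- *That no comparison of the boots is planned.* The ANOVA sentence shows that one is.
- *That the plan will analyse the boots as independent groups.* The structure is unstated; ignoring participants is a risk, not a declared method.
- *That ignoring participants would be safely conservative, or would always inflate false positives.* Steps 3 and 4 show that the direction depends on the model.
- *That the false-positive rate is 60%.* That needs separate subgroup tests, independence and an either-motion reading of 11.1. The wording of 11.1 can also be read as requiring both motions.
- *That the contrast was chosen after looking at the data.* The dates make this possible (see the fix), but nothing shows that it happened.

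**Conclusion.** The concern holds. The only sentence that designates a primary analysis names a calculation that cannot answer 11.1, and no ANOVA result is named as deciding it. This should be fixed; the design and the data remain usable.

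That conclusion needs no arithmetic. The figures only show that the open choices matter: a false-positive chance of roughly 8% to 60% across the readings in step 2, a loss of power from 91% to 73% in one unpaired analysis, and a type I error of about 1% to 19% in another. They rest on assumed correlations and variance shares, on 2.7 being a per-condition SD (step 3), and on a 2.1 difference that was not a between-boot difference.

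**What to change.** In section 11.3.2, replace the power-analysis sentence with text such as:

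> The primary analysis is a two-sided, within-participant comparison of the two boots. For each participant the ROM parameter is averaged over [named settings and tasks] to one value per boot, and the paired difference is tested, adjusting for boot order (equivalently, a repeated-measures ANOVA or mixed model with participant and participant-by-boot random terms). Hypothesis 11.1 is decided by this contrast for [one named sagittal ROM parameter] and for a_ROM invev, reported as differences with 95% confidence intervals; [either: Holm-adjusted across the two at 0.05, if one suffices; or: each at 0.05, if both are required].

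The sponsor fills the brackets and states whether the third setting enters the contrast. A participant random intercept alone must not be used on pooled cells (step 4). Keep the power calculation in section 11.2 only. Report the other section 5.1 outcomes without letting them decide 11.1, and align sections 5.1 and 11.3.3 and the synopsis.

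**Cost.** A few sentences, no change to data collection, and ethics committee approval, since section 2.9 counts a change in the form of statistical analysis as substantial. At an assumed correlation of 0.5, Holm leaves at least 84% power for one contrast instead of 91%. Requiring both motions also costs power: if each has 91%, joint power is at least 1 − 2 × 0.09 = 82%.

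**Timing.** Section 6.2 plans data analysis from February 2017, the study is unblinded (section 6.3.2), and version 3.0 is dated 08.03.2017. If boot comparisons have already been seen, the report must say that the contrast was fixed afterwards.
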